Proprietary confidential information.

© 2017 Boehringer Ingelheim International GmbH or one or more of its affiliated companies. All rights reserved.

This document may not - in full or in part - be passed on, reproduced, published or otherwise used without prior written permission.

- 5 Before any trial procedure, both the patient and/or parent/legal guardian have to give informed consent/assent according to the local regulatory requirements. At each moment along the trial, the site staff must disclose and discuss any new information that might affect willingness to continue trial participation with the patient and/or parent/legal guardian. For the MTD expansion cohorts/phase II part a high rate of screening failures is expected. Therefore a [pre-screening](#) informed consent may be used to allow collection and testing of tumour tissue for ErbB deregulations (see section [3.3.2](#)). Upon confirmation of positivity for selection biomarkers and before to proceed with trial procedures the informed consent/assent for trial entry, as mentioned earlier in this footnote, must be signed.
 - 6 Pulmonary examination must include transdermal O₂ saturation at screening, at visit 1 of each course and EOT. It should be repeated as clinically indicated during the trial and may be supplemented by a chest X-ray if clinically indicated.
 - 7 Measurement of height (in cm) will be performed on day1 every other courses.
 - 8 Safety lab tests should not be repeated if previous tests are not older than 48 hours.
 - 9 Safety lab test at visits 2, 3, 4 of courses 1 and 2 to be limited as described in [Section 5.2.3](#).
 - 10 Mandatory for female patients of child bearing potential (post menarchal) within 7 days prior to first treatment and at EOT. To ensure early detection of pregnancy, test might be repeated as necessary during the treatment period depending on the local law.
 - 11 ECG is required at screening, at C1V2, V1 every third course thereafter (i.e. C4V1, C7V1...) and EOT.
 - 12 Left ventricular ejection fraction (LVEF) at screening, at end of course 1 (C2V1 visit) and to be repeated C4V1, every 3rd course thereafter (C7V1...) and EOT.

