If a patient experiences DLT (for definition refer to [Table 4.1.4.1:2](#)), therapy may be continued at a reduced dose (for dose reduction, refer to [Table 4.1.4.3:1](#)) after recovery of the respective adverse event(s) to pre-dose CTCAE grade(s). The investigator shall liaise with BI and ask for confirmation of the dose of the trial drug before a new treatment course is started for any patient. In questionable cases, the DMC might be involved in decision making. If a patient is not eligible for further therapy, the patient has to discontinue further treatment with the trial drug.

Proprietary confidential information.

© 2017 Boehringer Ingelheim International GmbH or one or more of its affiliated companies. All rights reserved.

This document may not - in full or in part - be passed on, reproduced, published or otherwise used without prior written permission.

Table 4.1.4.1:2 Dose limiting toxicities

Dose limiting toxicity (DLT)

DLTs are defined as any of the following events that are considered related to afatinib:

1. CTCAE grade 4 hematologic toxicity lasting for 7 days
 2. CTCAE Grade 3 or 4 non-hematologic toxicity (except fever grade 3).
 3. CTCAE Grade 2 or higher decrease in cardiac left ventricular function
 4. CTCAE Grade 2 or higher worsening of renal function as measured by serum creatinine, newly developed proteinuria, or newly developed decrease in glomerular filtration rate
 5. CTCAE Grade 2 diarrhoea persisting for 7 or more days, despite supportive treatment (loperamide treatment or other effective anti-diarrhoeal medication)
 6. CTCAE Grade 2 nausea and/or vomiting persisting for 7 or more days despite antiemetic treatment
 7. CTCAE grade 5 events
-

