5.2.3 Assessment of safety laboratory parameters

Safety laboratory samples will be analyzed at the investigator's local laboratory. Safety laboratory examinations will include hematology, biochemistry and urine examinations. Table 5.2.3: 1 presents the laboratory tests to be performed at screening, Day1 of each course and/or EOT whatever applies.

Table 5.2.3:1 Clinical Laboratory Tests

Category	Parameters
Haematology	Haemoglobin (Hb), platelet count, white blood cell count (WBC), with differential (neutrophils, lymphocytes, monocytes)
Coagulation	International Normalized Ratio (INR), activated Partial Thromboplastin Time (aPTT)
Chemistry	
Electrolytes	sodium, potassium, calcium, magnesium, chloride, bicarbonate (HCO ₃)
Liver function tests	alkaline phosphatase, aspartate aminotransferase (AST), alanine aminotransferase (ALT), γ -glutamyltransferase (GGT), total bilirubin
Renal function parameters	Blood urea/blood urea nitrogen (BUN), creatinine; Creatinine clearance estimate by institutional standard formula for estimation of GFR in paediatric patients.
Category	Parameters
Other	glucose, albumin, phosphorus, lactate dehydrogenase (LDH), total protein, uric acid, creatine phosphokinase (CK); in case of pathological CPK further evaluation (e.g by determination of isoenzymes, troponin assays, ECG exam) should be performed as clinically indicated, CRP
Urinalysis	pH, protein, glucose, erythrocytes, leucocytes, nitrite and, if clinically indicated ketones, urobilinogen, specific gravity; in case of pathological finding(s) further evaluation should be performed and results of the latter must be documented
Pregnancy test	β -HCG testing in urine or serum in girls of childbearing potential (WOCBP)

Proprietary confidential information.

© 2017 Boehringer Ingelheim International GmbH or one or more of its affiliated companies. All rights reserved.

This document may not - in full or in part - be passed on, reproduced, published or otherwise used without prior written permission.

Limited lab tests (Hb, WBC, ANC, thrombocytes) will be required at intermediary visits

The investigator should complete additional evaluations of laboratory tests as clinically indicated. Any abnormal findings from these investigations need to be reported as an Adverse Event. For confirmation of laboratory findings indicative for drug induced liver injury (DILI), local laboratories will be used

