7.8.2 Laboratory data

The analyses of laboratory data will be descriptive in nature and will be based on BI standards (5). The same on-treatment period as considered for the analysis of AEs will be applied for laboratory values. CTC grade for applicable lab parameters will be calculated according to CTCAE v3.0 (7).

For a list of laboratory parameters considered for this trial, please refer to CTP Section 5.2.3, Table 5.2.3:1. Descriptive statistics of all normalized laboratory values by visit will be provided including changes from baseline. Transition tables of CTCAE grade from baseline to worst value and last value on treatment, and frequency tables of possible clinically significant abnormalities will be produced. For those parameters that have CTC grading possible clinically significant abnormalities are defined as those laboratory values with a CTC grade ≥ 2 that have had an increase of ≥ 1 grade from baseline. For those parameters for which no CTC grade has been defined standard BI project definitions will be used to decide on clinical significance. See [Tables 7.8.2: 1](#) and [7.8.2: 2](#) for the potential clinical significance rules.

Analyses of descriptive statistics will use normalized lab values (variables ULN, LABN). Analyses of frequencies of patients with potential clinical significance, analyses of shift, and liver function categories tables will use converted values (ULC, LABSTD).

Summaries will be produced of laboratory data recorded on-treatment. Listings will be provided for data recorded prior to treatment, on-treatment and post-treatment. For details on the treatment definition, see [Section 6.1](#).

For the primary laboratory parameters listed in Table 7.8.2: 1, full analysis of descriptive statistics, transition tables and possible clinically significant abnormalities will be conducted.

Analysis of secondary laboratory parameters listed in [Table 7.8.2: 2](#) will be limited to frequency tables of possible clinically significant abnormalities. Listings of converted and normalized values for all laboratory parameters considered for this trial will be provided in Appendix 16.2 of the CTR.

Table 7.8.2: 1 Primary laboratory parameters

Label	Lab test name	Direction of interest	Potential clinical significance rule
ALKP	Alkaline phosphatase	High	A ¹
APTT	APTT (Activated partial thrombopl. time)	High	A ¹
CRE	Creatinine	High	A ¹
CRECL	GFR/Creatinine clearance	Low	A ^{1,2}
HGB	Haemoglobin	Low	A ¹
INR	PT-INR	High	A ¹

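### Platelets are missing from the SAP's laboratory tables, so as written they get no grade-shift table and no Grade 2 or higher count, unlike Hb, WBC, neutrophils and lymphocytes

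*SAP*

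**What the plan says.** SAP 7.8.2 refers to protocol Table 5.2.3:1 for the laboratory parameters considered. It then makes two general statements. By-visit descriptive statistics, with changes from baseline, will be given for all normalised values. Grade-transition tables and frequency tables of possible clinically significant abnormalities will be produced; this second statement names no parameters. For graded parameters an abnormality counts if it is Grade 2 or higher and at least one grade above baseline. The two parameter tables are cited for these rules.

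Later in the same section, outputs are tied to the tables. "For the primary laboratory parameters listed in Table 7.8.2: 1, full analysis of descriptive statistics, transition tables and possible clinically significant abnormalities" are to be carried out, while the parameters of Table 7.8.2:2 are restricted to abnormality frequency tables. Listings for all parameters go to Appendix 16.2 of the trial report.

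The protocol treats platelets as a core safety test:
- Section 5.2.3, Table 5.2.3:1: the haematology panel is haemoglobin plus "platelet count, white blood cell count (WBC), with differential (neutrophils, lymphocytes, monocytes".
- Section 5.2.3, below that table: "Limited lab tests (Hb, WBC, ANC, thrombocytes) will be required at intermediary visits".
- Flow Chart, footnote 9: "Safety lab test at visits 2, 3, 4 of courses 1 and 2 to be limited as described in" Section 5.2.3.
- Section 4.1.4.1, DLT item 1: "CTCAE grade 4 hematologic toxicity lasting for 7 days".
- Section 3.3.3, exclusion criterion 15: bone marrow function is defined by ANC and platelets together.
- Section 7.3.3: all abnormalities of potential clinical significance are to be reported, in general those at Grade 2 or higher with a rise in grade from baseline.

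**The concern.** The tables give most blood counts an objective toxicity summary: how many patients moved to Grade 2 or worse on laboratory values alone. That count does not depend on anyone recording an adverse event. Platelets have no row, so a programmer working from the tables would produce no such count for them.

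For platelets the summary would then rest on the AE tables. Under protocol 5.2.2.1 a laboratory change becomes an AE if the investigator judges it clinically relevant; under 5.2.3, abnormal findings from additional evaluations must also be reported. By-visit means and quartiles do not show how many patients worsened by grade. A reader wanting that number would have to build it by hand from the listings.

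**Working it through.** The check compares lists; no power or sample-size formula applies, and the SAP states no total of its own to reproduce.

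**Rows in the SAP tables.** Table 7.8.2:1 has 14: ALKP, APTT, CRE, CRECL, HGB, INR, K, LYMPH, NA, NEUT, SGOT, SGPT, TBILI, WBC. Table 7.8.2:2 has 8: BUN, CA, CK, GLUB, LDH, TPRO, UREA, URIC. Together 14 + 8 = 22 distinct labels. Both lists are in unbroken alphabetical order, so nothing suggests a row lost in text extraction or blacked out.

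**Haematology tests in protocol Table 5.2.3:1 against the SAP tables.**

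| Test | In limited panel | In SAP Table 7.8.2:1 | In SAP Table 7.8.2:2 |
|---|---|---|---|
| Haemoglobin | yes | yes | no |
| WBC | yes | yes | no |
| Neutrophils (ANC) | yes | yes | no |
| Platelets | yes | **no** | **no** |
| Lymphocytes | no | yes | no |
| Monocytes | no | no | no |

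Coverage is 4 of 6 haematology tests and 3 of 4 limited-panel tests (75%). Platelets are the only limited-panel test left out, while lymphocytes, which are not in that panel, are included.

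**How often platelets are measured.** Scheduled post-baseline samples up to Course 3 Day 1 are Course 1 Days 8, 15 and 22 (3), Course 2 Days 1 and 15 (2), and Course 3 Day 1 (1): 3 + 2 + 1 = 6. By the end-of-Course-1 visit (Course 2 Day 1) there are 3 + 1 = 4. The data for a grade-shift table are therefore already scheduled.

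**Which sentence governs.** Suppose the general sentence on transition and frequency tables gave both outputs to every parameter. The later sentence restricting secondary parameters to frequency tables would then contradict it for all 8 of them. Reading the later sentences as the assignment removes the contradiction, and on that reading a parameter in neither table gets neither output. This is the better reading but not the only one: the general sentence and the general abnormality rule contain no explicit restriction.

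**Patients affected.** The denominator would be the treated set (SAP 7.8). The protocol plans 17 + 38 = 55 patients. The documents give no rate of Grade 2 or higher platelet falls that go unrecorded as AEs, so no patient count can be derived.

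**The case against.** The strongest reply is that SAP 7.8.2 already covers platelets. It adopts the protocol's full parameter list, says without restriction that transition and frequency tables will be produced, and gives a general rule for any graded parameter; the two tables are cited there for the significance rules. The section also rests on company laboratory standards (SAP references 5 and 6) that are not available here and may supply standard platelet tables. This stands as far as it goes: the text is ambiguous, and one cannot say flatly that no platelet table would be made. It does not remove the point, because platelets still have no row, direction of interest or listed rule, and the later sentences assign outputs by table.

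It can also be said that the list is selective by design, since monocytes, magnesium, GGT, albumin and others are absent too, and that listings for about 55 patients can be read by hand. Both are fair, and they keep the point small. Platelets differ from the other absent blood tests in being part of the limited panel and in their link to the haematologic DLT item; the SAP gives no reason for separating them from their companion counts.

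A reader might extend the point to urine protein. It too is in neither table (the total-protein row corresponds to the chemistry test), although urinalysis includes "pH, protein, glucose, erythrocytes, leucocytes, nitrite" and DLT item 4 includes "newly developed proteinuria, or newly developed decrease in glomerular filtration rate". The documents do not support treating it the same way. A count would need a mapping from local urinalysis results to CTCAE grades, and the documents neither give one nor say whether the results are quantitative. Protocol Table 5.2.3:1 already requires further evaluation of pathological urinalysis findings, with documented results. Leaving a possibly ungradable test out of a grade-based count is defensible.

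**Conclusion.** The point holds for platelets, as a minor matter with moderate confidence. On the table-based assignment in SAP 7.8.2, platelets get no more than by-visit descriptive statistics and listings, without the transition table and Grade 2 or higher count given to haemoglobin, WBC, neutrophils and lymphocytes. The size is one missing parameter out of four in the limited panel.

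This rests on three assumptions: that the later, table-specific sentences govern; that the unseen company standards do not fill the gap; and that platelets are gradable under CTCAE v3.0, as the graded haematologic DLT item implies.

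Two stronger inferences should be resisted. One is that protocol 7.3.3 is breached. That section requires abnormalities to be reported without saying which tests need a count or shift table, and all values are listed. The other is that DLTs could be missed or the MTD be wrong. DLTs are adverse events of special interest with expedited reporting (protocol 5.2.2.1 and 5.2.2.2) and are tabulated for the first course and all courses (SAP 7.4.1 and 7.8.1). The MTD had already been set at 80% of the adult dose (protocol 4.1.3). None of this depends on the laboratory tables, and efficacy is untouched.

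**What to change.** Add one row to SAP Table 7.8.2:1: platelets, direction of interest Low, potential clinical significance rule A. This places platelets beside the other limited-panel counts and settles the ambiguity for them. No urine-protein row is proposed.

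The cost is one table row and the corresponding programmed output. The data are already collected, grading by CTCAE v3.0 is already specified in SAP 7.8.2, and rule A matches the general definition in protocol 7.3.3. There is no real downside.

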© 2017 Boehringer Ingelheim International GmbH or one or more of its affiliated companies. All rights reserved.

This document may not - in full or in part - be passed on, reproduced, published or otherwise used without prior written permission.

- EGFR gene amplification (FISH): Either $EGFR/Cen7 \geq 2.0$ or $\geq 10\%$ of cells with ≥ 15 copies or $\geq 40\%$ of cells with ≥ 4 copies or gene cluster in $\geq 10\%$ of cells *and/or*
- HER2 gene amplification (DDISH): $Her2/CEP17 \geq 2.0$ *and/or*
- EGFR protein expression: H-score > 150 (membrane staining) *and/or*
- HER2 protein expression: H-score > 0 (membrane staining)

Inclusion will be based on biomarker assessment prior to inclusion, as detected by central laboratory analysis of tumour biopsy material

- Inclusion criterion #3: Patients aged between ≥ 1 to < 18 years
- Inclusion criterion #7: Archival and/or fresh tumour tissue available.

Inclusion criteria 2, 4, 5, 6, 8-12 apply as above

- Inclusion criterion #13: Patients with proven genomic, transcriptomic or proteomic ErbB alterations which are not defined in the above inclusion criterion #1 regardless of tumour histology (See [Section 5.6](#), [tables 5.6:1 to 5.6:4](#)).
- Inclusion criterion #14: Patients must have at least one measurable lesion according to the institutional response criteria for the given tumour type.

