K	Potassium	Low	A ¹
LYMPH	Lymphocytes	Low	A ¹
NA	Sodium	Low	A ¹
NEUT	Neutrophils	Low	A ¹
SGOT	AST/GOT, SGOT	High	A ¹
SGPT	ALT/GPT, SGPT	High	A ¹
TBILI	Bilirubin, total	High	A ¹
WBC	White blood cell ct.	Low	A ¹

¹A = CTCAE grade 2 or greater with an increase of at least one CTCAE grade from baseline.

²Values less than 0.25xLLN will be assigned CTCAE grade 3.

Table 7.8.2: 2 Secondary laboratory parameters

Label	Lab test name	Direction of interest	Potential clinical significance rule
BUN	Blood urea nitrogen	High	> 10
CA	Calcium	Low & High	A ¹
CK	Creatine kinase	High	A ¹
GLUB	Glucose	Low & High	A ¹
LDH	LDH	High	≥ 3xULN
TPRO	Protein, total	Low & High	< 45, > 100
UREA	Urea	High	> 1.5xULN
URIC	Uric acid	High	A ^{1,3}

¹A = CTCAE grade 2 or greater with an increase of at least one CTCAE grade from baseline.

³Values >ULN – 10 mg/dL or ≤0.59 mmol/L will be assigned CTCAE grade 1.

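### SAP Table 7.8.2:2 flags blood urea nitrogen by a fixed number and urea by a multiple of ULN, so one renal measurement is judged by two rules that do not match

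*SAP*

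**What the plan says.** Protocol section 5.2.3, Table 5.2.3:1, lists among the renal function tests "Blood urea/blood urea nitrogen (BUN), creatinine", so the slash offers urea and BUN as alternatives for one item. The same section states that "Safety laboratory samples will be analyzed at the investigator's local laboratory". Protocol section 3.3 expects about 30 sites in the EU, the US and Canada.

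SAP section 7.8.2, Table 7.8.2:2, carries the two forms as separate rows. The BUN row reads "Blood urea nitrogen High > 10" and the urea row reads "Urea High > 1.5xULN". The first is an absolute number without a unit. The second is relative to the laboratory's upper limit.

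Three other statements in SAP section 7.8.2 bear on how these rows are used:

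- On the source of the rules: "For those parameters for which no CTC grade has been defined standard BI project definitions will be used to decide on clinical significance".
- On the data used: the sentence that covers frequencies of potential clinical significance ends by saying that these and the "liver function categories tables will use converted values (ULC, LABSTD"), so site results are first put into a standard unit.
- On the extent of analysis: for secondary parameters it "will be limited to frequency tables of possible clinically significant abnormalities", apart from listings of all laboratory values in the report appendix.

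**The concern.** One physiological quantity gets an absolute rule under one name and a relative rule under the other. Which rule a patient meets is decided by the local laboratory's reporting form, not by anything about the patient. Two children with the same concentration and the same upper limit can be classified differently.

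For these parameters the frequency table is the only planned summary, so the inconsistency goes straight into what the report shows for urea and BUN. With up to 55 patients in the trial (Protocol section 3.3), split between two rows, reclassifying one or two patients would visibly change a percentage. A reader who adds the rows, or compares one with the other, would be combining figures that do not mean the same thing.

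**Working it through.** There is no derived figure in the plan to reproduce. Both cut-offs are stated rules, so the check is whether they are equivalent.

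**Inputs**
- BUN rule: more than 10, no unit (SAP Table 7.8.2:2).
- Urea rule: more than 1.5 × ULN (same table).
- ULN for urea or BUN: not in either document. Assumed here to be 5, 6, 7 or 8 mmol/L, for illustration only.
- Molar masses: urea 60.06 g/mol; the nitrogen in one urea molecule 28.014 g/mol. BUN in mmol/L is taken, as is usual, to count urea molecules, so BUN and urea in mmol/L are the same number.

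**Step 1: where the rules agree.** Reading 10 as mmol/L, set 1.5 × ULN = 10. Then ULN = 10/1.5 = 6.67 mmol/L. At any other limit the rules differ.

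**Step 2: size of the mismatch.** The BUN cut-off as a multiple of ULN is 10/ULN. The urea cut-off in mmol/L is 1.5 × ULN.

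| Assumed ULN (mmol/L) | BUN cut-off as multiple of ULN | Urea cut-off (mmol/L) | Values classified differently (mmol/L) |
|---|---|---|---|
| 5 | 10/5 = 2.00 | 7.5 | above 7.5 to 10: flagged as urea only |
| 6 | 10/6 = 1.67 | 9.0 | above 9.0 to 10: flagged as urea only |
| 7 | 10/7 = 1.43 | 10.5 | above 10 to 10.5: flagged as BUN only |
| 8 | 10/8 = 1.25 | 12.0 | above 10 to 12.0: flagged as BUN only |

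For example, at ULN 5 a value of 8 mmol/L (8/5 = 1.6 × ULN) is counted if reported as urea and not if reported as BUN. At ULN 8 a value of 11 mmol/L (11/8 = 1.38 × ULN) is counted as BUN and not as urea.

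**Step 3: does conversion to standard units cure it?** No. Converting multiplies a result and its limit by the same factor k, and (k × value)/(k × ULN) = value/ULN. A rule set as a multiple of ULN is therefore unaffected by units. A fixed cut-off stays fixed after conversion and still ignores the limit. No other provision in either document links the two rows.

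**Step 4: what the missing unit could mean.** 10 mmol/L is 10 × 28.014/10 = 28.0 mg/dL of BUN. Conversely, 10 mg/dL is 100/28.014 = 3.57 mmol/L. The two readings differ by a factor of 2.8.

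**The case against.** The strongest reply is that little turns on this, and much of that reply stands. Urea and BUN are secondary laboratory parameters. Creatinine and GFR/creatinine clearance are primary ones, with descriptive statistics, CTCAE shift tables and abnormality tables (SAP Table 7.8.2:1). The renal DLT and dose-reduction criteria in Protocol section 4.1.4 rest on creatinine, proteinuria and GFR. SAP section 7.8.1 groups acute renal failure with severe diarrhoea as an adverse event category, and individual values are listed in the report appendix. The rules also come from the sponsor's project definitions, and neither document shows that 1.5 × ULN is intrinsically the better limit for BUN.

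A reader might infer four stronger points that the documents do not support:

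- **Age bias.** The expansion part admits "Patients aged between ≥ 1 to < 18 years", and it is tempting to conclude that a fixed cut-off treats younger children differently. That needs a urea limit that varies with age. Neither document gives one; the exclusion criteria mention age adjustment for bilirubin and creatinine only.
- **One count mixing two thresholds.** The SAP keeps the rows separate and nowhere pools them. The supportable point is that they cannot be compared or added.
- **A cut-off of 10 mg/dL that flags low values.** This is unlikely. The table is run on converted values, and total protein in the same table also has limits without a unit, which suggests a layout convention. The omission is a gap in the text, not evidence of a wrong threshold.
- **A lost renal safety signal.** The other renal analyses and the listings cover this.

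What survives the reply is the non-equivalence itself. Citing a project definition says where the rules came from, not why one measurement has two.

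**Conclusion.** The two rows apply non-equivalent rules to forms that the protocol treats as interchangeable, and the unit of the BUN cut-off is not stated. Whether a value is flagged depends on the form reported and on the laboratory's ULN. This follows from the documents plus the molar identity of the two forms, for any ULN other than 6.67 mmol/L when 10 is read as mmol/L.

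The size shown, 2.0 down to 1.25 × ULN against a constant 1.5, rests on assumed limits of 5 to 8 mmol/L. How many patients would be reclassified cannot be estimated, because the documents give neither the laboratories' limits nor the split between forms.

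The consequence is confined to a descriptive safety table. It touches no endpoint, DLT, dose rule or sample size. It is worth correcting because correction is nearly free, not because a conclusion of the trial is at risk.

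**What to change.** In SAP Table 7.8.2:2, apply one reporting rule to both forms. Convert BUN and urea to mmol/L, flag either at more than 1.5 times the reporting laboratory's ULN, as the table already does for urea, and tabulate them as one parameter, counting a patient with both forms once. State the unit of any fixed cut-off that remains in the table. This changes a reporting flag only and implies nothing about patient management.

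The cost is one table cell and a conversion step. Upper limits are already needed for the urea and LDH rows. The documents do not say whether the stored limits are age-specific, and the fix does not require it. The downside is that one parameter departs from the sponsor's project definition, which a footnote can record. If the sponsor prefers to keep both rules, the SAP should state the unit, give the reason, and note that the two rows are not comparable.
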